# 5. Study Interventions and Concomitant Therapy

## 5.1 Drug information

### 5.1.1 Drug Administration

Patients with HPV positive CIN2/3 will receive 3 cycles of oral artesunate 200mg OD prior to therapeutic large loop excision transformation zone (LLETZ). Each treatment cycle comprises 21 days, with oral artesunate 200mg OD given for 14 days followed by a 7 day treatment break.

### 5.1.2 Premedication

No premedication is required.

### **5.1.3 Patient Monitoring**

Baseline temperature, blood pressure, heart rate, oxygen saturations and electrocardiogram will be recorded prior to commencing the IMP. Baseline temperature, blood pressure, heart rate, oxygen saturations will be repeated at each study visit whilst on IMP or as requested by the PI as clinically indicated.

### **5.1.4 Treatment duration**

Patients with HPV positive CIN2/3 will receive 3 cycles of oral artesunate 200mg OD prior to therapeutic large loop excision transformation zone (LLETZ). A treatment cycle comprises 21 days, with oral artesunate 200mg OD given for 14 days followed by a 7 day treatment break.

### **5.1.5 Dose and schedule modifications**

No dosage modifications will be undertaken. Any Grade 3/4 reaction (according to Common Terminology Criteria for Adverse Events (CTCAE) Version 5.0) which occurs in any patient and is deemed related to the IMP by the treating investigator will result in that patient's trial treatment being discontinued. If patients develop Grade 3 neutropenia or more (according to the Common Terminology Criteria for Adverse Events (CTCAE) Version 5.0) they should be managed with granulocyte colony stimulating factor (GCSF) supplied via routine hospital pharmacy in accordance with local policy and prescribing practice. The study drug will be stopped and they will continue to be monitored until their full blood count recovers. They will not be recommenced on the study drug but will continue to be followed up within the trial.

### **5.1.6 Packaging and storage conditions**

Study medication will be provided in bottles. One bottle will provide 28 tablets – sufficient for the duration of 1 cycle of treatment. The product labelling will be fully compliant with both Appendix E: Labelling Requirements of the Rules and guidance for Malaysian-Guideline-for-Application-of-CTIL-and-CTX-7.1-Edition and the protocol submitted and authorised by the NPRA.

### **5.1.7 Pregnancy**

Artesunate is teratogenic in animal models and is contraindicated in the first trimester of pregnancy in humans. Pregnant women with malaria nevertheless are exposed to artesunate when no alternatives are available for treatment and studies published to date do not indicate an increased risk of teratogenicity. Pregnant women will not be recruited and participants will be required to use effective methods of medical contraception during the study. Women of child bearing age will be required to undergo a pregnancy test within 72 hours prior to commencing the study and must consent to adequate contraceptive methods from the time of consent and for up to 6 weeks following the end of IMP treatment.

### **5.1.8 Adverse events associated with artesunate**

Artesunate has a good safety profile and has been taken by millions of patients worldwide for malaria. In data taken from studies of malaria, serious side-effects are extremely rare. However the average treatment duration of artesunate in malaria is 3-5 days. In our Phase II study, the treatment duration of 14 days for 3 cycles represents a prolonged duration of treatment compared to conventional treatment for malaria and therefore requires close pharmacovigilance.

The Summary of Product Characteristics for Artesunate provided to sites lists the potential side

effects. The reference safety information document provided to sites lists the adverse events considered by the Sponsor as being 'expected'.

### **5.1.9 Source of IMP**

Bulk artesunate 100 mg tablets are manufactured by HCM- Medical under license according to Good Manufacturing Practice (GMP).

Artesunate is packaged into bottles containing 28 tablets. Package labelling was performed under controlled conditions to ensure no cross contamination. HCM- Medical performed the controlled labelling operation.

Each bottle has a label affixed in accordance with Appendix E: Labelling Requirements of the Rules and guidance for Malaysian-Guideline-for-Application-of-CTIL-and-CTX-7.1-Edition

The named Qualified Person (QP) at HCM- Medical will issue a QP release certificate. The full IMP batch will be delivered, accompanied by the QP batch release certificate to the study sites.

Upon instruction from the Sponsor, HCM-Medical will arrange an appropriate delivery to each participating trial site of sufficient artesunate. Shipment will be under temperature-controlled conditions and the recipient pharmacy department at each site will be required to confirm by return of a completed delivery note as instructed that correct shipment conditions have been maintained. A copy of the QP release will be provided to each site to file in the Pharmacy Site File (PSF).

Full IMP accountability will be maintained at all participating site pharmacy departments or Clinical Research centres.

The IMP artesunate 100 mg tablets must be stored below 25°C. Temperature records are to be maintained with daily minimum/maximum readings via a calibrated/certified thermometer. The records will be available for monitoring visit purposes and either a copy of those records or a signed statement of compliance will be placed in the Pharmacy Site File (PSF) following the end of IMP treatment phase.

### **5.1.10 Accountability procedures for the IMP**

Each participating site's pharmacy department or research centre will be responsible for maintaining and updating the IMP Accountability Log, filed in the pharmacy site file. All used/unused IMP(s) will be returned to the site pharmacy. If a research pharmacist is not available at the study site, a qualified study coordinator that is not part of the investigator's team can perform this task.

IMP(s) destruction will be conducted, following verification by the Clinical Trials Monitor and agreement by the Sponsor, in accordance with local pharmacy practice. Destruction records will be maintained and filed in the PSF.

## **5.2 Concomitant therapy**

There are no reports of negative drug interactions with artesunate to date. Concomitant medication details will be collected at baseline and any changes recorded at subsequent study visits. The CI will monitor the international literature for drug interactions and report any emerging data to the study sponsor and as part of the annual Development Safety Update Report (DSUR). The study protocol and concomitant medication allowed on study will be updated accordingly.

If patients develop Grade 3 neutropenia or more (according to the Common Terminology Criteria for Adverse Events (CTCAE) Version 5.0) they should be managed with granulocyte colony stimulating factor (GCSF) supplied via routine hospital pharmacy in accordance with local policy and prescribing practice.

### **5.3 Withdrawal criteria**

Patients may discontinue study treatment or withdraw their consent to participate in the study at any time without prejudice. In consenting to the trial, participants are consenting to trial treatments, trial follow up and data collection. However, an individual participant may stop treatment early or be stopped early for any one of the following reasons :

- Unacceptable treatment toxicity or an adverse event
- Investigator decides that it is in the best interests of the patient to terminate his/her participation in the study
- Poor patient compliance and/or major protocol deviation
- Intercurrent illness that prevents further protocol treatment

#### Withdrawal of consent from the participant

As participation in the trial is entirely voluntary, the participant may choose to discontinue treatment at any time without penalties or loss of benefits to which they may be entitled. Although not obliged to give a reason for discontinuing their trial treatment/study participation a reasonable effort should be made to establish this reason, whilst remaining fully respectful of the participant's rights. Participants who discontinue protocol treatment, for any of the above reasons, should remain in the trial for the purpose of follow up and data analysis.

Temporary discontinuations of study medication are not permitted. If a patient decides to discontinue treatment then the patient's decision should be documented on the Subject Tracking log, CRF and the IMP returned to the study site Pharmacy or research centre. Participants should continue to be followed up as closely as possible to the follow-up schedule defined in the protocol, providing they are willing. However if the participant confirms they do not wish to participate in the scheduled follow up data collection visits then data that has already been collected should be kept and analysed according to the ITT principle for all participants who stop follow up early. Patients withdrawn from the study will continue to be followed up according to the study protocol to the scheduled date of study completion, or to recovery or stabilisation of a followed-up Adverse Events (AE), whichever comes last. Routine medical and surgical care of withdrawn participants will continue as planned. The investigator will make every effort to contact the participant in the case of non attendance to a planned review appointment. Participants who stop the trial follow up early will not be replaced.

Participants who develop CTCAE v5.0 Grade 3 or 4 serious adverse effects related to artesunate will be withdrawn from the study treatment but will continue in the study to enable an intention to treat analysis.

There will be a 24 hour emergency card provided to each participant when they receive their IMP dispensed from pharmacy. The 24 hour emergency card will contain the contact details of the local PI and site team in addition to a NeoART-CIN 24 hour emergency telephone number.

All PIs and research team members will have appropriate experience and knowledge of the target patient population. All team members will have demonstrated experience in clinical research and Good Clinical Practice (GCP).

The Chief Investigator (CI) and the CI delegate will construct a Trial Master File and ensure that all essential trial documents are stored safely and securely. The trial will be subject to monitoring in accordance with the Sponsor risk-based monitoring plan. The purpose of the monitoring is to ensure the safety, rights and well being of the trial participants are upheld and that any risk to the trial data is minimised.

## **5.4 Assessment of compliance**

If vomiting occurs during the course of treatment, the dose should not be retaken on the same day. The occurrence and frequency of any vomiting during the reporting period must be noted in the adverse events log and CRF. Each treatment cycle will comprise artesunate 200mg once a day for 14 days followed by a 7 day break. Patients will receive 3 cycles of treatment. At each treatment cycle, an assessment of medication compliance will be made by the principal investigator or delegated research team member on Day 7, Day 14, Day 22, Day 43 and Day 64 based on verbal answers given to direct questioning. This data will be entered into the Case Report Form. Following completion of the patient's IMP treatment period any unused medication will be returned to the site pharmacy department or research centre for the IMP accountability log to be updated. Patients who take the study drug for < 8 days in a 14 day treatment period will be considered 'non-compliant'. All patients will continue to be followed up according to the study protocol regardless of compliance.

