#### 1.2.2 Secondary outcome measures

- HPV DNA viral clearance at Day 90.
  - Viral clearance will be defined as absence of HPV genotype (s) detected at baseline.
- Vaginome and gut microbiome at Day 1, Day 64 and Day 90.
  - Changes in vaginome and gut microbiome will be compared between Day 1, Day 64 and Day 90.
- Serious Adverse Events at Day 90 using Common Toxicity Criteria (CTCAE V5.0).
  - Safety assessment will be based on patients who received at least one dose of IMP.
- Tolerability assessment will be based on the percentage of subjects that complete the designated dosing regime.

- Patient quality of life using the European Quality of Life–5 Dimensions (EQ-5D) quality of life tool Day 1, Day 7, Day 14, Day 22, Day 43, Day 64 and Day 90.

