## 6.4 Summary table

Study Procedures	Screening prior to study entry	D1 Clinical review prior to start of medication	D7 Telephone consultation	D14 Clinical Review	D22 Clinical Review	D36 Telephone consultation	D43 Clinical Review	D57 Telephone consultation	D64 (+3 days) Clinical Review	D90 (+14 days) Clinical Review
Consent	X									
Medical History	X	X		X	X		X		X	X
Clinical Examination	X	X			X		X		X	X
Telephone consultation review			X			X		X		
Toxicity Assessment			X	X	X		X		X	X
Concomitant medication check		X	X	X	X		X		X	
Patient self-reported events (diary card)			X	X	X		X		X	X
Vital signs		X		X	X		X		X	X
Pregnancy Test		X								
Study medication check				X			X		X	
Safety Blood Test (FBC/renal/liver profile)		X		X	X		X		X	X
Study Blood test		X		X					X	X
Speculum examination					X		X		X	
Colposcopy examination + Cervical Biopsy		X								X
HPV Test		X							X	X
Vaginome + gut microbiome sample		X							X	X
Large Loop Excision Transformation Zone (LETTZ)										X
QOL Tools (EuroQol EQ-5D)		X	X	X	X		X		X	X

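### Compliance is scored from verbal answers alone; the returned tablets, which map directly onto the plan's own thresholds, are not stated to be used

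*Protocol*

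**What the plan says.** Section 5.4 assesses compliance "on Day 7, Day 14, Day 22, Day 43 and Day 64", "based on verbal answers given to direct questioning", and enters the result in the CRF. It sets the cut-off: "Patients who take the study drug for < 8 days in a 14 day treatment period will be considered 'non-compliant". Once a patient has finished treatment, "any unused medication will be returned to the site pharmacy department or research centre for the IMP accountability log to be updated". No other use of the returned tablets is stated.

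Section 5.1.10 adds: "All used/unused IMP(s) will be returned to the site pharmacy". It also allows IMP to be destroyed after the monitor has verified it and the sponsor has agreed. Section 5.1.6 says "One bottle will provide 28 tablets", enough for one cycle, and section 5.1.9 gives the tablet strength as 100 mg.

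Two analysis definitions depend on dose-taking. In section 1.2.2, repeated in 10.2.4, "Tolerability assessment will be based on the percentage of subjects that complete the designated dosing regime". In section 10.2.1 the per-protocol set requires 8 or more of the 14 cycle 1 doses.

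The table in section 6.4 has a row "Study medication check" marked at D14, D43 and D64. Its content is not described.

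**The concern.** A patient's spoken answer is the only compliance method that the protocol describes. It is applied to an oral regimen taken at home, which section 5.1.8 itself calls prolonged compared with use in malaria. A patient who has missed doses and does not say so is recorded as having taken them. That error runs mainly one way, towards better apparent compliance.

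Three outputs are exposed: the tolerability percentage, the compliance and exposure summaries of section 10.2.2, and membership of the per-protocol set. The interim looks in section 10.1.1, which review feasibility and tolerability, are exposed as well.

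A more objective source passes through the site pharmacy anyway, but nothing requires its count to reach the CRF. After destruction the tablets cannot be recounted. This is a matter of what is collected, so it is better settled in the protocol than left to the analysis stage.

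**Working it through.** **Inputs.** Dose 200 mg once daily for 14 days, three cycles of 21 days (section 5.1.1). Tablets of 100 mg (5.1.9). 28 tablets per bottle, one bottle per cycle (5.1.6). Cut-off of 8 days or doses out of 14 (5.4, 10.2.1). At most 28 patients (Protocol Summary).

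**Reproducing the pack size.** (200 / 100) × 14 = 28 tablets per cycle, as stated; 28 × 3 = 84 over three cycles.

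**From count to threshold.** With two tablets per dose, tablets left = 28 − 2 × doses taken.

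| Doses taken | Tablets left | Reading under the plan's definitions |
|---|---|---|
| 14 | 0 | cycle complete |
| 8 | 12 | just meets the cut-off |
| 7 | 14 | non-compliant |

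So 12 or fewer left means at least 8 doses, and 14 or more left means non-compliant. A count of 13 does not fit whole doses and would need a query.

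**Recall interval.** Dosing runs over about D1–14, D22–35 and D43–56. For cycle 2 the first listed assessment after dosing ends is D43, and 43 − 35 = 8 days. For cycle 3 it is D64, and 64 − 56 = 8 days. Section 5.4 lists no assessment during dosing in cycle 2, or in cycle 3 after its first day (D43). The telephone contacts at D36 and D57 are not on its list.

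**Day lists.** Section 5.4 has D7, D14, D22, D43 and D64. The 6.4 row has D14, D43 and D64. D7 and D22 appear only in 5.4, and D7 is a telephone contact.

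**Effect per patient.** One misclassified patient moves the completion percentage by 1/28 = 3.6 points at the end, by 1/14 = 7.1 points at the second interim look and by 1/3 = 33.3 points at the first.

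**Illustration.** The protocol gives neither a completion rate nor an over-reporting rate, so both are assumed here. Suppose 22 of 28 truly complete, and some of the 6 non-completers are recorded as completers. Intervals are exact (Clopper–Pearson) 95%.

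| Non-completers recorded as completers | Reported | Percentage | 95% CI |
|---|---|---|---|
| 0 of 6 | 22/28 | 78.6 | 59.0 to 91.7 |
| 2 of 6 | 24/28 | 85.7 | 67.3 to 96.0 |
| 3 of 6 | 25/28 | 89.3 | 71.8 to 97.7 |
| 6 of 6 | 28/28 | 100 | 87.7 to 100 |

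The last row is a ceiling. It requires every non-completer to go undetected.

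**The case against.** **Many non-completions do not depend on recall.** Investigators stop treatment for related Grade 3/4 reactions and for Grade 3 or worse neutropenia (section 5.1.5). A patient's decision to stop is documented on the tracking log and CRF, and temporary interruptions are not permitted (5.3). This stands. A reader might infer that the whole tolerability measure rests on memory. It does not: only undisclosed missed doses are exposed.

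**There may already be a physical check.** The 6.4 row falls once at or after the end of dosing in each cycle, which would suit a tablet count. If it is one, the day lists need not conflict, because they would describe different procedures. This stands too. The documents do not show that tablets are never counted, only that no such use is stated. Equally, they do not show that the row is a count, and section 5.4 does not mention it.

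**A count at the end of each cycle is not in the protocol.** Section 5.4 times the return after the whole treatment period, and 5.1.10 gives no timing. The pack size makes a count by cycle possible, but only if bottles are kept apart or counted at visits.

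**A count is not ingestion.** Tablets lost or discarded would be scored as taken. This argues for reconciling two sources, not for replacing one with the other.

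**The derivation may be in the SAP.** The protocol does not say in terms that the completion percentage or the per-protocol set draws on the verbal answers. That is inferred from verbal questioning being the only method described and from the shared 8-of-14 cut-off. A SAP can fix the derivation, but it cannot supply a count that the CRF never received.

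**The per-protocol set carries little weight.** Section 10 defines it but assigns no analysis to it, and its dose criterion concerns cycle 1 only. This is fair, and it limits the stakes.

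**Conclusion.** The point holds as an inexpensive improvement to data collection. Verbal answers are the only stated basis for scoring compliance, while the packaging and return arrangements permit a count that matches the plan's own thresholds. The effect is confined to the tolerability percentage, the compliance and exposure summaries, and per-protocol membership. The regression percentage in the intention-to-treat set does not use compliance and is unaffected.

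The firm figure is 3.6 points per misclassified patient at 28 patients. A reader might go further and apply an assumed over-reporting rate to all 28 to obtain a total bias. The documents do not support that: only true non-completers can over-report completion, their number is unknown, and those who stop for toxicity or by declared choice are recorded separately. The likely direction is upward, but the size cannot be stated.

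The conclusion assumes two tablets per dose, one bottle per cycle, and that completion and the 8-of-14 criterion are taken from the compliance data of section 5.4.

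**What to change.** In section 5.4:

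- Keep each cycle's bottle separate and enter the number of tablets returned, per bottle, in the CRF.
- Score compliance and regimen completion from that count reconciled with the verbal report: 0 left for a complete cycle, 12 or fewer for at least 8 doses, 14 or more for non-compliant. Query a count of 13, and any disagreement between the two sources.
- Use the verbal report alone when a bottle is not returned, and flag those patients.

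In section 6.4, state whether the medication check is this count, and reconcile its three days with the five in 5.4. A count on D14 may precede that day's dose, so the timing of the cycle 1 count should be made explicit.

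The cost is transcription of a count and some bottle handling, with no added visit. Lost tablets will still be counted as taken, and reported compliance may look slightly worse.

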## **5.5 Overdose of Trial medication**

In the event of an overdose of trial medication the patient should attend the Accident and Emergency and be urgently reviewed by a member of the research team during working hours or the on-call Medical Officer. A thorough medical history and events leading to the overdose should be documented as well as a complete physical examination including blood pressure monitoring. Blood tests should be performed including full blood count, urea and electrolytes and liver function tests. There is no antidote or documented role for gastric lavage. The overdose should be documented in the participants medical notes and CRF. The Adverse Event log and the Serious Adverse Events (SAE) reporting form should be completed. The completed SAE form should be emailed to the Sponsor in accordance with the protocol.

## **5.6 List of criteria for premature discontinuation of the study**

The study may be discontinued prematurely by the Sponsor, the Data Monitoring Committee(DMC) or the Chief Investigator (CI) if:

- As a result of the interim analysis or any other event during the study there is significant doubt based on statistical evaluation as to the risk/benefit ratio
- The aim of the study has become outdated or is no longer of interest
- There is a serious breach by the investigator of a fundamental obligation under this agreement, including but not limited to breach of the Study Protocol, breach of the applicable laws and regulations or breach of the ICH guidelines for Good Clinical Practice

In all cases the relevant ethics committee and NPRA will be informed in accordance with statutory guidance.

## 5.7 Lost to Follow up

For all participants that consent and are enrolled in the trial, information in relation to their Next of Kin (NoK) details will be confirmed as correct and current in the patient medical records to facilitate ease of contact throughout the study and data collection period. Following a missed scheduled visit, effort to contact the participant and/or Next of Kin on up to 3 occasions over a 7-10 day period should be made. Each occasion will be documented in the medical notes and on the Telephone log.

